7.7 Procedures for Pausing the Trial

Upon review of the safety data from the trial, the DSMB will make decisions regarding the continuation of the trial. The DSMB will conduct an initial review after study drugs are distributed to approximately 10 participants in each treatment arm and consider halting or stopping the study if 1 or more participants in any treatment arm experiences an SAE by month 3 after treatment. The DSMB will pause to review data after any SAE then start again following the review and determination of the study’s safety. Because participants will be recruited as cohorts, safety evaluations will be held on an ongoing basis and include cumulative safety data of grade 1 and 2 AEs and specific case information for grade 3 and above.

The DSMB has been convened to look out for the safety of study participants; it has the right and responsibility to pause the study if any of the treatments is associated with an unacceptable frequency of serious or severe adverse events. The DSMB should consult with the study medical monitor and PI before making a final decision to suspend the study. If the DSMB recommends discontinuation or modification of the study, the Chair of the DSMB will meet or speak to the DOLF Project Team at the earliest opportunity to review the basis for the recommendation, and the DOLF Project team will notify the Principal Investigator. The DSMB will begin data review meetings after enrollment of participants in the investigational arms of this study.

The DSMB and IRB/ERCs have the authority to stop the study at any point. The study may also be terminated by regulatory bodies if there is significant violation of GCP that compromises the ability to achieve the primary study objective or compromises subject safety.

However, as DSMB members are not on site, it is appropriate that they get input from the medical monitor and PI before making stopping or pausing decisions. The DSMB Chair will communicate the decision to discontinue or modify the study with the DOLF Project Team and the DOLF Project Team will immediately notify the PI of the DSMB's decision. The DOLF Team is in a better position to communicate with the DSMB Chair (only 1 hour time zone difference, more reliable internet, etc.).

8 STATISTICAL CONSIDERATIONS

8.1 Sample Size Determination (Power calculation)

The *primary outcome* variable used for our power analysis is the % fertile female worms (100 x fertile female worms/ total female worms) for each of the three drug treatments: (1) single-dose IVM (IVM alone); (2) single dose of IVM + DEC and albendazole (IDA1); (3) three daily doses of IVM + DEC and albendazole (IDA3). Power calculations for our primary treatment-group comparison (IVM /ALB vs IDA1) assumed that 30% of the total worms will be fertile females in IVM/ALB group and that 15% of the total worms will be fertile females in the IDA1 group. For our secondary treatment-group comparison (IVM/ALB vs IDA3), we assumed that 10% of the total worms were fertile females for the IDA3 group. On average, we assumed that there will be 6 total female worms to evaluate in 3 nodules per person after treatment. In our analysis we treated each worm within a subject as a Bernoulli trial (0=non-fertile female worm, 1=fertile female worm), and we used an intra-class correlation (ICC) of 30% to account for within subject correlation among the trials. The ICC and cluster size (# female worms/person) adjusts the sample-size estimate using the following formula: $1 + \text{ICC} \times (\text{Cluster size} - 1)$ ^{44, 45}. To achieve 80% power at a two-sided alpha-level of 0.05, we will need nodule histology data from 51 subjects in each treatment group for the primary treatment-group comparison (IVM/ALB vs IDA1). The expected % difference for our secondary treatment-group comparison (IVM/ALB vs IDA3) powered at 80% and an alpha of 0.05, would require 26 subjects/group. After accounting for a 20% drop-out rate, a sample size of at least 61 subjects per treatment group will enable us to address both the primary (IVM/ALB vs IDA1) and secondary (IVM/ALB vs IDA3) treatment-group comparisons. Furthermore, we will attempt to enroll additional subjects beyond the target of 61 to provide some protection against other (unforeseen) factors that could decrease the power of this study (e.g., within village correlation, smaller effect size, higher drop-out rate than anticipated). The study will provide preliminary safety data, but a much larger study will be required to provide a precise safety comparison of IVM/ALB vs IDA.

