4.2 Inclusion and Exclusion Criteria

Inclusion Criteria

1. Men and women 16 – 70 years (at the time of enrollment; ± 2 years) of age previously enrolled in the Part 1 study and residing in the area of the study.
2. Participants must have at least 1 palpable subcutaneous nodule (onchocercoma).
3. Participants with baseline skin Mf counts ≥ 3 Mf/mg at the time of enrollment into the Part 1 study (Part I, see above).

Exclusion Criteria

1. Pregnant and breastfeeding mothers within 1 month of giving birth
2. Severe eye disease at baseline including uveitis, severe glaucoma, , severe keratitis, and/or cataracts that interfere with visualization of the posterior segment of the eye as well as the list of ocular diseases as outlined below Individuals who are excluded with significant ocular disease will be referred to appropriate ophthalmological care in a health facility (the district hospital) or the any other health facility in Ghana, where affected subjects will obtain appropriate care (University hospital or private ophthalmologist). All ocular disease exclusion criteria apply to either eye. Bilateral disease is not necessary to exclude a participant. A participant will be excluded if any of the criteria are met for one eye.
 - a. Any cataract of any type preventing clear visualization of fundus or imaging on Optical Coherence Tomography (OCT).
 - b. Severe retinal nerve fiber layer thinning in the superior and inferior quadrant analysis on Ocular Coherence Tomography of the optic nerve with a corresponding visual field defect of grade 2 or worse on the same eye.
 - i. If Ocular Coherence Tomography is not available, the following exclusion criteria will apply: vertical Cup/disc ratio on fundoscopy (not by OCT reading) greater than or equal to 0.80.
 - c. Intraocular pressure (IOP) greater than or equal to 25 by Goldmann tonometry.¹²
 - d. Retinal Detachment or Retinal Break
 - e. Acute ocular infection (i.e., Viral conjunctivitis, corneal ulcer, endophthalmitis)
 - f. Optic Atrophy with visual field defect reproducible on confrontation visual field testing..
 - g. Exam consistent with Herpes Simplex Virus eye infection
 - h. Homonymous hemianopsia, quadrantsopsia, bitemporal hemianopsia, or central scotoma related to cerebral vascular disease by Automated Visual Field testing and confrontation visual field testing.
 - i. Acute Angle Closure Glaucoma
 - j. Gonioscopy grade 0 (slit) limiting ability to safely dilate patient

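### Section 8.1 treats an average of 6 female worms per person as a constant, so 51 evaluable per group gives somewhat less than the stated 80% power once worm counts vary

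*Combined protocol and SAP*

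**What the plan says.** Section 8.1 takes the percentage of female worms that are fertile as the primary outcome and treats each worm as a Bernoulli trial nested in a person.

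- Error rates: "To achieve 80% power at a two-sided alpha-level of 0.05".
- Fertile worms: "30% of the total worms will be fertile females in IVM/ALB group", "15% of the total worms will be fertile females in the IDA1 group" and, for the secondary comparison, "10% of the total worms were fertile females for the IDA3 group".
- Clustering: "we used an intra-class correlation (ICC) of 30% to account for within subject correlation among the trials".
- Cluster size: "On average, we assumed that there will be 6 total female worms to evaluate in 3 nodules per person after treatment". No SD, CV or range accompanies this average.
- Adjustment: "The ICC and cluster size (# female worms/person) adjusts the sample-size estimate using the following formula", followed by 1 + ICC x (cluster size - 1).

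The results are 51 evaluable per group for IVM/ALB vs IDA1 and 26 for IVM/ALB vs IDA3. After drop-out the section sets a minimum of 61 per group. It adds that the study will try to enrol more as protection against unforeseen losses of power. Section 4.1 caps enrolment at 300.

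Three other places bear on worm counts. Section 4.2 sets the entry rule: "Participants must have at least 1 palpable subcutaneous nodule (onchocercoma". Section 8.2 analyses enrolled persons who have a nodulectomy at 18 months and sets no minimum worm count. Section 8.2 also specifies a binomial mixed model with a random effect for person.

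**The concern.** The design effect in section 8.1 has no term for variation in cluster size. At ICC 0.30, a person with m female worms contributes information worth m / (1 + 0.30 x (m - 1)) independent worms. This rises quickly for the first few worms and then flattens: 1.54 at m = 2, 2.40 at m = 6 and 2.70 at m = 10. People with few worms therefore lose more than people with many worms gain. Any spread around a mean of 6 reduces the total, even under the most efficient weighting.

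The direction of the error is thus certain, and only its size is open. At 51 evaluable with a constant 6 worms the margin above 80% is 0.6 of a point, so there is almost nothing to absorb the loss. The stake is the power quoted for the primary efficacy comparison at the size the plan presents as sufficient. This is separate from how drop-out is added to 51.

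**Working it through.** **Inputs from section 8.1.** 30% vs 15% fertile (primary), 30% vs 10% (secondary), two-sided alpha 0.05, power 80%, ICC 0.30, mean 6 female worms per person.

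**Step 1: reproduce the plan's figures.** Worms per group if independent:

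n = [1.960 x sqrt(2 x 0.225 x 0.775) + 0.842 x sqrt(0.30 x 0.70 + 0.15 x 0.85)]² / 0.15² = 120.5, rounded up to 121.

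Design effect = 1 + 0.30 x 5 = 2.5. Then 121 x 2.5 / 6 = 50.4, so 51. For 30% vs 10%, 62 x 2.5 / 6 = 25.8, so 26. Both stated figures reproduce, and both use a constant 6.

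**Step 2: power at 51 with exactly 6 worms each.** Effective worms = 51 x 6 / 2.5 = 122.4.

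Power = Φ[(0.15 x sqrt(122.4) - 1.960 x 0.5906) / 0.5809] = 80.6%.

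**Step 3: let worm counts vary, mean kept at 6.** The protocol gives no spread, so the distributions below are assumptions. Effective worms per person = E[m / (1 + 0.30 x (m - 1))], which approximates the weighting of the planned mixed model.

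Worked case: 1 to 5 nodules equally likely, 2 female worms in each (CV 0.47). The mean of 1.538, 2.105, 2.400, 2.581 and 2.703 is 2.265, against 2.400 for a constant 6. Then 51 x 2.265 = 115.5 effective worms and power is 78%. The number needed is 120.5 / 2.265 = 53.2, so 54.

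| Assumed worm counts (mean 6) | CV | Power at 51 evaluable | Evaluable per group for 80% |
|---|---|---|---|
| Constant 6 | 0 | 80.6% | 51 |
| Poisson | 0.41 | 79% | 53 |
| 1-5 nodules, 2 worms each | 0.47 | 78% | 54 |
| Negative binomial | 0.5 | 78% | 54 |
| Negative binomial | 0.7 | 76% | 57 |
| Negative binomial | 1.0 | 71% | 64 |

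The negative binomial at CV 1.0 places 11.6% of people at zero female worms (3.6% at CV 0.7). That is missing outcome data rather than unequal cluster size. Restricting to positive counts with the same mean and CV gives 78%, 76-77% and 73-74% at CV 0.5, 0.7 and 1.0, with about 54, 56 and 60 needed. Hence the ranges 71-73% and 60-64 at CV 1.0.

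**Step 4: pessimistic bound.** The cruder design effect 1 + ICC x ((1 + CV²) x m - 1), which weights people by worm count, is 2.95, 3.38 and 4.30 at CV 0.5, 0.7 and 1.0. Power at 51 is then 74%, 68% and 57%.

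**Step 5: larger enrolment.** 300 / 3 = 100 per arm, and 100 x 0.8 = 80 evaluable. Efficient-weighted power is about 93% at CV 0.5, 92% at 0.7 and 88% at 1.0. The crude bound stays at or above 80% up to a CV of about 0.9 and is 77% at CV 1.0. If only 61 per group enrol and 20% are lost, 61 x 0.8 = 48.8, about 49, remain. Efficient-weighted power is then 77%, 74% and 69% at CV 0.5, 0.7 and 1.0.

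**Step 6: secondary comparison.** For IDA3, 51 evaluable gives 86% or more up to CV 1.0 even under the crude bound.

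**The case against.** The strongest reply is that nothing is miscalculated. The section says openly that 6 is an average, and using a mean in a design effect is a common planning approximation. The loss rests on a CV that the documents do not supply. At moderate spread it is about 2 to 5 points, and other inputs matter as much: with constant clusters at 51, an ICC of 0.35 gives 77% and an IDA1 rate of 16% gives 74%. The plan also treats 61 as a floor and allows up to 300.

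Most of this stands, and it limits the size of the point. It does not restore 80% at 51, because the direction does not depend on the CV. The enrolment margin does not settle it either. The 300 is a ceiling, enrolment beyond 61 is only to be attempted, and the margin is reserved for unforeseen factors. Variation in worm count can be foreseen from the entry rule.

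Two stronger readings are tempting and are not supported:

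- **That the trial as a whole fails to deliver 80%.** At 80 evaluable per arm, efficient-weighted power is above 80% in every case examined.
- **That the one-nodule entry rule shows the mean of 6 to be wrong.** One nodule is a minimum and is compatible with an average of three. A lower mean would be a different problem, and nothing in the protocol shows it.

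The 57-74% figures should likewise be read as a bound, since the planned model does not weight people simply by worm count.

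**Conclusion.** The point holds in a limited form. 51 per group gives 80% power only if every evaluable person yields exactly 6 female worms. With worm counts that vary around 6, power at 51 is modestly below 80%: about 79% at CV 0.4, falling to 71-73% at CV 1.0. The corresponding need is about 53 rising to 60-64 evaluable per group.

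This assumes a mean of 6, a common ICC of 0.30, marginal rates of 30% and 15%, an assumed CV range, and efficient weighting as an approximation to the mixed model. The shortfall has practical effect only if enrolment stops near 61 per group. The IDA3 comparison is little affected.

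**What to change.** Recompute section 8.1 allowing for unequal worm counts, either by simulating the planned mixed model or by using the efficient-weighting information formula over a stated CV range. State the assumed CV and its source. Section 4.6 says baseline palpation information exists from the Part I study. If it includes nodule counts it can inform the spread, though it will not give female worms per nodule; otherwise show a range such as 0.4 to 1.0. Report separately any allowance for people with no evaluable female worm, so that it is not mixed with cluster-size variation or drop-out. Restate power at 51, 61 and 100 per arm, saying for each whether the number is enrolled or evaluable, and stop describing 51 as giving 80%.

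The cost is a rewrite of section 8.1 and a stated power a few points less favourable at the minimum size. No enrolment beyond the 300 already allowed is needed.

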4.1 Study Design

This is an open label, randomized clinical trial will be conducted in Ghana. The goal will be to enroll up to 300 eligible participants with microfiladermia. Some participants who have met the inclusion criteria (see Study Enrollment, below) will have intraocular Mf visible by slit lamp at baseline prior to IVM pre-treatment. Participants will be recruited from an on-going related study that is evaluating the kinetics of Mf clearance from the eye and skin after treatment with IVM. Participants will be treated with ivermectin at baseline in this study and then randomized into three treatment arms 6 months (with a window of 5.5 months to 12 months) after treatment with IVM:

1. IVM with albendazole (the comparator)
2. A single dose of IDA
3. Three daily doses of IDA

Each arm will be stratified with respect to the presence ocular Mf six months after their first IVM pre-treatment (i.e. in “Part I”, a preceding study) or at the baseline assessment in the Part II study. Participants will be closely monitored to determine whether the treatments are safe. Efficacy will be assessed by performing skin snips for detection of Mf and by histological examination of adult worms in onchocercal nodules surgically removed 18 months after treatment with IDA.

All participants will be treated again with ivermectin at the time of consenting for the Part II study to further ensure that they have low skin and ocular Mf counts at the time of enrollment and randomization to treatment arms. Treatment with ivermectin is widely accepted as a standard of care for MDA programs, and should not present undue risk.

Study Enrollment

Participants will be recruited from an on-going related study of the kinetics of Mf clearance from skin and eyes after ivermectin treatment (Part I). Participants from that study with baseline skin Mf counts ≥ 3 Mf/mg will be invited to participate in this “Part II” study.

Study Population - Participants will be recruited from the Nkwanta North and South Districts in the Volta region of Ghana. Most participants will be recruited from Kpassa town or villages in Kpassa sub-district along the Kpassa river basin that are endemic for onchocerciasis. Residents are mainly of the Konkomba ethnic group. The local language is Konkomba, however most residents also speak and understand the Twi language. Bi-annual MDA with IVM in the area started in October 2017. The target number of participants for the study will be up to 300.

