Note that the samples sizes per treatment group in this study are not sufficient to provide a robust safety profile (e.g., high confidence that the rate of SAEs after treatment is less than 0.1%). This proof of concept study will allow for initial safety assessments to be performed. Additional, larger studies will be required to establish a more complete safety profile. The safety assessments put in place for this study along with the frequent and ongoing review by the DSMB will provide a strong foundation to evaluate the participant's safety throughout the study.

Data from all participants in this study will be analyzed for safety and efficacy outcomes. The study population for the primary and secondary endpoints related to adult worm viability and fertility are persons who were enrolled and who have nodulectomies performed 18 months after treatment. The study population for secondary efficacy outcomes related to microfilariae in the skin are participants who were enrolled in the study who have follow-up microfilaria testing by skin snip examination at time points (12, 18 months) as indicated in the diagram on page 26 of the protocol. The study population for the early (7 day) safety analysis are participants who receive the study drugs who have safety assessments during the 7 days after dosing. A separate safety analysis will consider data from the follow-up examinations conducted 3 months after dosing.

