11.5 Withdrawal

Entry into the study and participation will be strictly voluntary. It will be made clear that refusal to participate or a decision to withdraw can occur at any time throughout the course of the study and will not influence their rights or the care they receive at local health facilities.

In two of the three treatment arms the participants receive a single treatment. In the 3rd treatment arm the patients receive treatment on three consecutive days. While there is no dose titration in place the investigator has the discretion to discontinue treatment if the treatment appears to be creating distress to the participant. The study investigator would monitor these participants closely and assess any adverse events that have occurred. There is no plan in place for the study investigator to re-initiate treatment once it has been discontinued.

Withdrawal from the study can be at the participant or investigator discretion at any time during the trial. All subjects that withdraw from the study will be encouraged to complete the safety follow-up visits (daily for 7 days after dosing and at 3 months).

Data collected on the participant up to the point of withdrawal remains part of the study database. If the participant withdraws from the interventional part of the study and agrees to continue being seen for the safety follow-up visits the associated clinical outcome information such as medical information and laboratory results will be part of the study database.

There is no plan to replace withdrawn participants.

Protocol deviations are collected through the electronic data capture system (i.e. visits out of window, in-appropriate dosing, etc.) and reviewed through the tables, figures, listings. Additionally, a Protocol Deviation Log has been put in place to address deviations not picked up by EDC. Participants who fail to report for follow-up examinations will not be considered to have withdrawn, and the study team will attempt to contact them for follow-up testing at later time points listed in the protocol.

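### Section 8.1: a minimum of 61 per group does not cover the stated 20% drop-out; keeping the plan's own 51 evaluable subjects takes 64 (power about 79% instead of 80% at 61)

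*Combined protocol and SAP*

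**What the plan says.** Section 8.1 sizes the trial on the percentage of female worms that are fertile, with each worm treated as a Bernoulli trial clustered within its host. The design targets are given as: "To achieve 80% power at a two-sided alpha-level of 0.05". For the primary comparison the plan states that "we will need nodule histology data from 51 subjects in each treatment group"; for the secondary comparison (IVM/ALB vs IDA3) it gives 26 per group. The enrolment minimum follows: "After accounting for a 20% drop-out rate, a sample size of at least 61 subjects per treatment group", described as sufficient for both comparisons.

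The next sentence says that "we will attempt to enroll additional subjects beyond the target of 61 to provide some protection against other (unforeseen) factors". The examples it lists are within-village correlation, a smaller effect, and more drop-out than expected.

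Three other statements bear on the point:
- Section 8.2 defines the population for the worm endpoints as "persons who were enrolled and who have nodulectomies performed 18 months after treatment".
- Section 11.5 says: "There is no plan to replace withdrawn participants".
- Section 4.1 says: "The target number of participants for the study will be up to 300".

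**The concern.** A drop-out rate is the share of enrolled subjects who are lost. If a fraction d is lost, the number to enrol is the number needed divided by (1 − d). Multiplying the number needed by (1 + d) gives too few, because the loss applies to the larger, enrolled number. The step from 51 to 61 looks like the multiplication.

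The 51 is a count of subjects with histology, and the worm endpoints are analysed only in people who have the 18-month nodulectomy. Each person lost before then therefore comes straight off the 51. At stake is whether the only enrolment minimum in the sample-size section delivers the plan's stated power at the plan's stated drop-out rate.

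**Working it through.** **Inputs (section 8.1).** Two-sided alpha 0.05; power 80%; fertile share 30% with IVM/ALB, 15% with IDA1 and 10% with IDA3; 6 female worms per person; ICC 0.30; drop-out 20%. Section 4.4 gives equal allocation to the three arms.

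**Step 1. Reproduce the plan's evaluable numbers.** The design effect is 1 + 0.30 × (6 − 1) = 2.5. The pooled two-proportion formula without continuity correction, with p̄ = (p1 + p2)/2, gives the number of independent worms per group:

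n = [1.960 × √(2p̄(1 − p̄)) + 0.842 × √(p1(1 − p1) + p2(1 − p2))]² / (p1 − p2)²

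- 30% vs 15%: n = 120.5 worms. Subjects = 120.5 × 2.5/6 = 50.2, rounded up to **51**. This matches the plan.
- 30% vs 10%: n = 61.6 worms. Subjects = 61.6 × 2.5/6 = 25.7, rounded up to **26**. This matches the plan.

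Both published figures come out exactly, so the fault lies only in the drop-out step.

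**Step 2. The drop-out step.**
- 51 × 1.20 = 61.2, which matches the stated 61.
- 51/(1 − 0.20) = 63.75, so **64** per group (192 in total, against 3 × 61 = 183).
- 61 × 0.80 = **48.8** evaluable, 2.2 below the 51 required.
- 64 × 0.80 = 51.2 evaluable, which meets 51.
- Largest loss that 61 can absorb: 1 − 51/61 = 16.4%.
- Starting from the unrounded requirement: 50.2/0.80 = 62.75, so 63. That is still above 61.

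**Step 3. Power at the resulting numbers.** The same formula is solved for power, with effective worms per group = subjects × 6/2.5. For 48.8 subjects this is 117.12 worms.

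| Enrolled per group | Evaluable after 20% loss | Power, 30% vs 15% | Power, 30% vs 10% |
|---|---|---|---|
| 61 | 48.8 | 78.9% | 97.3% |
| 64 | 51.2 | 80.8% | 97.8% |
| 100 (ceiling of 300) | 80 | 94.4% | 99.9% |

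In whole subjects, 48 evaluable gives 78.2% and 49 gives 79.0%. At exactly 51 the figure is 80.6%.

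**The case against.** The strongest reply is that the gap has no practical consequence. It costs about one percentage point of power, which is less than the uncertainty in the planning inputs. With 48.8 evaluable subjects, power is back at 80% if the ICC is 0.286 instead of 0.30, or if there are about 6.7 worms per person instead of 6, and both inputs are round assumptions. The trial also aims for up to 300 participants, and three more per group would close the gap. All of this is right, and it limits the severity. It does not make the sentence correct. The 300 is an upper limit, section 8.1 itself calls 61 the target, and the surplus is attempted, not committed. Section 8.1 assigns that surplus to other contingencies, including drop-out above the anticipated rate, so the anticipated 20% should already be inside the 61.

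A second reply is that the plan prints no drop-out formula, so the multiplication is inferred. That stands as a point about cause. The unpooled-variance version of the formula even comes close: 49.06/0.80 = 61.3. But that version implies 50 evaluable subjects, not the stated 51, and would round up to 62. In any case the shortfall does not depend on how 61 was reached, since 61 × 0.80 is below 51.

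Third, not replacing withdrawals is the ordinary premise of any drop-out allowance and does not enlarge the shortfall. That is also right. Section 11.5 only confirms that nothing elsewhere makes up the loss.

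**Conclusion.** The concern holds as a minor error in a stated number. On the plan's own figures the minimum is 3 per group too low (9 over three arms). A trial that stopped at 61 per group and lost the expected 20% would have slightly less than the stated 80% power for the primary comparison. The secondary comparison is not affected. The power figures rest on the plan's assumed rates, ICC and worms per person, on equal loss in every arm, and on the pooled formula that reproduces both 51 and 26. The shortfall against 51 rests only on the 61 and the 20%. This does not show that the trial as intended is underpowered: enrolment well above the minimum removes the problem.

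**What to change.** Make one of two changes in section 8.1.

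(a) Preferred: restate the minimum as 64 per treatment group, show the calculation 51/(1 − 0.20) = 63.75, and change the target in the following sentence from 61 to 64. This alters one number in two places and adds 3 subjects per group to the stated minimum (192 in total), well within the ceiling of 300.

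(b) Keep 61 and add a sentence saying that, with 20% drop-out, it leaves about 49 subjects per group with nodule histology and about 79% power for IVM/ALB vs IDA1. This costs one sentence, but leaves a minimum that knowingly misses the plan's own 51.

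Neither option changes the design, the analysis or the enrolment ceiling.
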